**c. Psychosocial (non-medical) risks**

There is a potential risk of loss of privacy. We will protect privacy by labeling samples, information, and data files only with a study subject number code and keeping the key to the code in a password protected database.

## **8. Benefits**

**a. Potential Benefits to subjects**

There are no medical or health benefits to subjects for participating in the study.

**b. Potential Benefits to Society**

Information gathered from this study may improve pain management during blood draw for patients in the future and improve our understanding of new ways to provide analgesia to the skin without topical or injectable numbing medication.

## **9. Statistical Analysis**

Pain Scoring Analysis

The Wong-Baker FACES Pain Rating Scale will be used to score subject pain in visit 1.

©1983 Wong-Baker FACES Foundation. [www.WongBakerFACES.org](http://www.WongBakerFACES.org)  
Used with permission. Originally published in *Whaley & Wong's Nursing Care of Infants and Children*. ©Elsevier Inc.

---

Statistical methods

The study is intended to gather empirical data about the pain assessment of the treatment area. Descriptive statistics will be collected to present quantitative descriptions of the pain level comparisons between the two hands.

In order to achieve a power of 0.95 with a p-value < 0.05, a sample size of 16 subjects is needed. This is assuming a standard deviation of 2 on the Wong-Baker Pain Rating scale, which will be used as the primary clinical outcome measure. A two-sided, independent t-test will be used to determine if any significant statistical difference is present between the pain level of each treatment arm using the absolute difference between the control and experimental pain scores.

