## **3. General Description of Study Design**

This is a self-controlled single-site study of 12 healthy subjects. The novel Cooling Device for Pain Management will be applied to the subject's finger, and a blood draw will be performed. The study includes blood amount quantification and a pain score report to evaluate the pain caused by the prick. Study subjects will be asked to do one visit of approximately 1 hour.

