## **4. Subject Selection**

Subjects will be screened to determine if they meet all the eligibility criteria specified below.

We will recruit and screen up to 20 subjects with the goal of having 12 subjects enroll and complete the study.

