#### *Visit 1*

Visit 1 is expected to last approximately 1 hour.

The following assessments will be performed during Visit 1:

- Review of eligibility criteria
  - Ring size measurement
- Review of medical history and medications
  - Urine pregnancy test (for female participants of childbearing potential)
- Take blood pressure (2 times before treatment; 2 times after) using a standard hospital owned blood pressure arm cuff device.
- The novel digit cooling device will be turned on and allowed to chill to -3 degrees Celsius prior to the procedure.
- Two fingers (one on each hand) will be pricked during Visit 1: the “control” digit and the “chiller” digit.
  - The first finger to be pricked will be randomized.
  - The pricked fingers will be either the fifth or third digit(s).

- Pricks will be administered using a sterile and disposable McKesson Push-Button 17G or 23G Safety Lancet, bought specifically for this trial.
- Subjects will be instructed on how to report a pain score for each prick. A visual 10-point pain scale will be used (see below).
- The procedure for the “control” digit is as follows:
  - A Beurer oximeter will be used to measure the percent oxygen and pulse rate.
  - A thermal camera will be used to measure the temperature of the finger tip.
  - One prick will be applied to the ventral tip of the “control” digit. A pain score will be reported by the subject.
  - The pricked finger will subsequently be held over a single-use Whatman 903 filter paper. Approximately every ten seconds after the prick, the filter paper will be gently applied to the blood drop to absorb the blood. This will be repeated on new locations of the filter paper until blood flow stops. At least one Whatman 903 filter paper will be used per finger prick. The Whatman 903 filter paper will be imaged.
- The procedure for the “chiller” digit is as follows:
  - A sterile glove will be placed on the “chiller” hand. The top of the fifth or third finger of the glove will be cut and rolled down to the base of the finger to promote venostasis and blood harvesting.
  - A Beurer oximeter will be used to ensure there is not enough blood flow to measure the percent oxygen and pulse rate in the finger.
  - A thermal camera will be used to measure the temperature of the finger tip.
  - A layer of glycerol will be applied circumferentially to the intended treatment area on the “chiller” digit.

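### Section 9 ties 95% power to 16 subjects, Sections 3 and 4 plan 12, and no target difference is given

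*Combined protocol and SAP*

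**What the plan says.** Section 9 (Statistical methods) makes the power claim: "In order to achieve a power of 0.95 with a p-value < 0.05, a sample size of 16 subjects is needed". It adds one input, "This is assuming a standard deviation of 2 on the Wong-Baker Pain Rating scale", and names the test: "A two-sided, independent t-test will be used to determine if any significant statistical difference is present", "using the absolute difference between the control and experimental pain scores". That last phrase identifies what is compared but gives it no magnitude.

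The design sections give another number. Section 3: "This is a self-controlled single-site study of 12 healthy subjects". Section 4: "We will recruit and screen up to 20 subjects with the goal of having 12 subjects enroll and complete the study".

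Each subject supplies both scores. Under Visit 1 in Section 6, "Two fingers (one on each hand) will be pricked during Visit 1", one as control and one chilled.

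**The concern.** There are two separate gaps.

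- **The numbers disagree.** The size said to be needed is 16 and the size planned is 12, a difference of 4, or 4/16 = 25%. Section 4 already deals with attrition by screening up to 20 to obtain 12 completers, so the 20 does not supply the missing 4.
- **The 16 has no visible derivation.** A sample size for a comparison of means needs a target difference and an SD of known meaning. Section 9 gives no difference, and its SD could be that of one score or of the within-subject difference.

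A reader therefore cannot tell what pain difference the primary comparison can detect, or with what power. A non-significant result in 12 subjects could be read against an assurance of 95% that was never worked out for 12. Staff also have two figures for when enrolment is complete.

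**Working it through.** **Inputs.** From Section 9: power 0.95, two-sided alpha 0.05, SD 2, n = 16. From Sections 3 and 4: n = 12. Not given anywhere: the target difference, what the SD refers to, and the within-subject correlation.

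**Method.** Power comes from the noncentral t distribution, with d the true difference divided by the SD.

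- Paired, n subjects: df = n − 1, noncentrality d√n, with the SD being that of the difference.
- Independent, n scores per arm: df = 2n − 2, noncentrality d√(n/2), with the SD being that of a single score.

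**Step 1: try to reproduce 16.** Without a target difference this cannot be done directly. It can only be solved backwards: which differences make 16 the smallest size reaching 95%? The lower end of each range gives exactly 95% at 16. The upper end is where one subject fewer (15 paired), or one score fewer per arm (15 or 7), would be enough. Multiplying d by SD 2 gives points.

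| Reading of the 16 | d for 95% power | Points |
|---|---|---|
| (a) 16 pairs, SD 2 of the difference | 0.9655 (n = 16), 1.0025 (n = 15) | 1.93 to 2.00 |
| (b) independent test, 16 scores per arm | 1.3175 (16), 1.3641 (15) | 2.64 to 2.73 |
| (c) independent test, 8 per arm, 16 in total | 1.9413 (8), 2.1035 (7) | 3.88 to 4.21 |

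All three return 16. Readings (a) and (b) fit 16 subjects who each give two scores. Reading (c) does not fit the self-controlled design, but that does not show it was not used. Two round targets also work: 2 points with 16 pairs (power 0.962) and 4 points with 8 per arm (power 0.960).

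**Step 2: keep the test and the difference, and reduce 16 to 12.**

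| Reading | Power at 12 subjects |
|---|---|
| (a) 12 pairs | 0.860 to 0.884 |
| (b) 12 scores per arm | 0.869 to 0.891 |
| (c) 6 per arm | 0.857 to 0.906 |

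Under (a) and (b) the chance of missing the difference is about 11% to 14% instead of 5%; under (c) it is about 9% to 14%. The detectable difference at 95% power grows by 1.1460/0.9655 = 1.187 under (a) and 1.5408/1.3175 = 1.169 under (b).

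**Step 3: 12 subjects under a paired test.** If SD 2 is of a single score and the correlation is r, the SD of the difference is 2√(2(1 − r)). The values of r are assumptions.

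| r | SD of difference | Power for 2 points | Power for 2.64 points | Detectable at 95% |
|---|---|---|---|---|
| 0 | 2.83 | 0.608 | 0.837 | 3.24 |
| 0.3 | 2.37 | 0.760 | 0.939 | 2.71 |
| 0.5 | 2.00 | 0.883 | 0.986 | 2.29 |
| 0.7 | 1.55 | 0.982 | 0.9996 | 1.78 |

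The row r = 0.5 is also the case where SD 2 is of the difference. For 4 points at r = 0 the power is 0.993. The 2-point figures at r = 0 and 0.3 show sensitivity only: with those inputs 16 pairs would not reach 95% either, so they cannot be what lies behind the 16.

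**The case against.** The strongest reply is that 12 may be enough. The power loss in step 2 keeps whatever test produced 16. If that was an independent test and the data are instead analysed as pairs, 12 can do better than 95%. Under (b) with a paired test, 95% is reached once the correlation is about 0.34 (2.64 points) or 0.29 (2.73 points). Under (c), 12 pairs give at least 99% even at zero correlation. Only (a) leaves a shortfall in every case. This stands: it rules out saying that 12 is definitely too few. It does not rescue the sentence in Section 9, which attaches 0.95 to 16 subjects and to an independent test.

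A second reply is that 16 is 12 plus dropout, since 12/0.75 = 16. No dropout rate is stated, however, and Section 9 presents 16 as the number needed for power.

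A third is that this is a small study in healthy volunteers whose statistical section opens in descriptive terms, and that 86% to 91% is still respectable power. That bears on the consequences. But the same section names a primary outcome, a two-sided significance test and a power, so those statements have to fit the planned study.

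Finally, no calculation has been shown to be wrong: 16 is neither confirmed nor refuted. That is correct. The defect is an inconsistency plus a missing assumption.

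**Conclusion.** The concern holds. The 0.95 is attached to a sample size that the plan does not enrol, and it cannot be checked because the target difference and the meaning of the SD are missing. If 16 is correct for some difference, the same test at 12 has about 86% to 91% power for it across the three readings. This assumes a two-sided alpha of 0.05, SD 2 and approximately normal scores or differences. Power for 12 under a paired analysis is unknown from the documents: it falls below 95% under reading (a), may fall either side under (b), and is above 95% under (c). The point should be fixed before the power statement is relied on.

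**What to change.** Make Sections 3, 4 and 9 give one number. Whichever number stands, Section 9 should state the sponsor's target difference, whether SD 2 is of a single score or of the within-subject difference (with the assumed correlation if it is of a single score), and the source of the SD.

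- **If 12 stands (the default).** Replace the 16-subject sentence with the power for 12 subjects under a two-sided paired t-test, since both scores come from the same person, or with the difference detectable at a stated power. Only if the sponsor confirms that SD 2 is of the difference could the text say that 12 subjects give 88% power for 2 points and 95% power for 2.3 points. If it is of a single score, the last column of the step 3 table applies. The cost is wording only, and the stated power may turn out below 95%.
- **If 12 is the outdated figure.** Change Sections 3 and 4 to 16. This costs 4 more subjects (4/12, one third more), and room under the screening cap falls from 20 − 12 = 8 to 20 − 16 = 4 screen failures or dropouts.

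### The primary pain test is an independent t-test, but every subject gives both scores, so the data are paired and the sentence cannot be run as written

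*Combined protocol and SAP*

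**What the plan says.** Section 9 (Statistical Analysis, Statistical methods) makes the Wong-Baker score the primary outcome and names one test: "A two-sided, independent t-test will be used to determine if any significant statistical difference is present" between the treatment arms, "using the absolute difference between the control and experimental pain scores". The same section promises "quantitative descriptions of the pain level comparisons between the two hands". On sample size it says: "In order to achieve a power of 0.95 with a p-value < 0.05, a sample size of 16 subjects is needed", with an assumed SD of 2. It gives no target difference and no correlation, and does not say whether the SD belongs to a single score or to a within-subject difference.

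The design is described elsewhere:

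- Section 3: "This is a self-controlled single-site study of 12 healthy subjects".
- Section 6.a, Visit 1: "Two fingers (one on each hand) will be pricked during Visit 1", one as control and one with the chiller.
- Section 6.a, Visit 1: "The first finger to be pricked will be randomized". This is the only randomization in the plan; subjects are not allocated to arms.
- Section 6.a, Visit 1: "Subjects will be instructed on how to report a pain score for each prick".

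No paired, one-sample or signed-rank test appears in the document.

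**The concern.** The two scores come from the same person, on the same scale, at the same visit. They are likely to be correlated, and an independent t-test assumes that they are not.

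The sentence also conflicts with itself. A two-sample test needs two samples, but the control-minus-chiller difference is one number per subject. To get a result, the analyst must ignore either the word independent or the clause about the difference.

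The word absolute adds a third reading. It may mean a difference on the raw scale, or a difference without its sign. The unsigned version loses the direction of effect. It is also never negative, so testing its mean against zero is not a test of the treatment.

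This is the plan's only inferential test, applied to the primary outcome with 12 planned completers. If the wording stays open, the choice of test could be made after the scores have been seen.

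**Working it through.** **Inputs.** From section 9: two-sided 0.05, power 0.95, SD 2, N = 16. From sections 3 and 4: 12 completers. Assumed, because the plan gives neither: a true difference of 2 to 4 points and a within-subject correlation ρ of 0 to 0.7.

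**1. Does the stated N of 16 show which test was meant?** No target difference is stated, so N = 16 cannot be reproduced directly. Solving noncentral-t power for the difference that N = 16 implies, with SD 2:

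| Reading of N = 16 | Implied difference |
|---|---|
| Paired test, SD of differences 2 | 1.93 points |
| Independent test, 16 scores per arm | 2.64 points |
| Independent test, 8 per arm | 3.88 points |

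In the other direction, a paired test at 2 points with SD of differences 2 needs 15.06, rounded up to 16. An independent test at 2 points needs 27 per arm. At 4 points it needs 8 per arm, which is 16 in total. So 16 fits either test and does not settle the matter.

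**2. Why the independent test miscalibrates.** With score SD σ and n pairs:

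- true variance of the mean difference: 2σ²(1 − ρ)/n
- variance that the independent test assumes: 2σ²/n

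The ratio of assumed to true variance is 1/(1 − ρ). At ρ = 0.5 it is 2, so the standard error is too large by a factor of √2 = 1.41.

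**3. Independent test on the two columns of scores, against the paired test.** Simulated bivariate normal scores, score SD 2, pooled-variance independent t-test, true difference 2 points for power:

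| n | ρ | Type I error, independent | Power, independent | Power, paired |
|---|---|---|---|---|
| 12 | 0 | 0.050 | 0.65 | 0.61 |
| 12 | 0.3 | 0.022 | 0.67 | 0.76 |
| 12 | 0.5 | 0.009 | 0.70 | 0.88 |
| 12 | 0.7 | 0.002 | 0.73 | 0.98 |
| 16 | 0 | 0.050 | 0.78 | 0.75 |
| 16 | 0.3 | 0.021 | 0.82 | 0.88 |
| 16 | 0.5 | 0.008 | 0.85 | 0.96 |
| 16 | 0.7 | 0.001 | 0.90 | 1.00 |

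The paired test holds 0.05 throughout.

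**4. Confidence interval half-width at ρ = 0.5.** The SD of differences is 2 × √(2 × 0.5) = 2.

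- n = 12, independent: 2.074 × 2 × √(2/12) = 1.69. Paired: 2.201 × 2/√12 = 1.27.
- n = 16, independent: 2.042 × 2 × √(2/16) = 1.44. Paired: 2.131 × 2/√16 = 1.07.

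**5. If SD 2 is the SD of the difference.** The score SD is then 2/√(2(1 − ρ)). At n = 12 and 2 points, paired power is 0.88 at any correlation. Independent-test power is 0.91, 0.83, 0.70 and 0.42 at ρ = 0, 0.3, 0.5 and 0.7.

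**6. Larger assumed effects.** With score SD 2, ρ = 0.5 and n = 12, independent against paired power is 0.98 against 0.997 at 3 points. At 4 points both are 1.00 to two decimals.

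**7. Unsigned reading.** A one-sample t-test of |control − chiller| against zero, with no true effect and normal scores, rejects in more than 99.9% of trials at n = 12 and at n = 16.

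**The case against.** An independent t-test can be computed mechanically on the two columns of scores, and the clause about the absolute difference might only name the effect measure on the raw scale. On that reading the sentence can be run, and the error is conservative when the correlation is positive: it yields too few false positives. The power loss depends on an assumed effect of about 2 points and almost disappears at 3 to 4 points. At zero correlation the independent test is valid and slightly stronger. The study is also small and described largely in descriptive terms.

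Much of this stands as a limit on size. The power loss is conditional, and the two-column analysis does not inflate false positives when the correlation is positive. It does not rescue the sentence. The two-column test is still the wrong one for paired data, and it is reached only by taking the difference clause as something other than the test's input. The wider confidence interval does not depend on the effect size; it needs only enough positive correlation. The unsigned reading is not conservative at all. The case for changing the text therefore rests mainly on a primary test that does not fit the design and can be read in several ways, and less on any one power figure.

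**Conclusion.** The concern holds, and the text must be corrected before pain scores are analysed. The design is paired, the named test is for independent groups, and the sentence read in full cannot be executed.

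The size depends on the reading. For the two-column test with score SD 2, correlation 0.5 and n = 12, type I error falls to 0.009, the interval is about a third wider (1.69/1.27 = 1.33), and power at an assumed 2 points drops by 0.18. The power loss is negligible at 4 points, and the order reverses slightly at zero correlation. For a one-sample test of the unsigned difference, a significant result is almost certain whether or not the device works. Effect, correlation and normality of the scores are assumptions; the mismatch between test and design is not.

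**What to change.** Replace the test sentence in section 9 with: *The primary analysis is a two-sided paired t-test on the signed within-subject difference in pain score (control minus chiller), reported with its 95% confidence interval.* The words independent and absolute go. In the sample-size text, state the assumed difference and say whether SD 2 refers to a score or to the within-subject difference, so that the calculation matches the paired test.

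A Wilcoxon signed-rank test, and a linear model on the differences with prick order coded ±0.5, could be added as sensitivity analyses. Neither is needed to correct the defect.

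The cost is one sentence, plus one line on the sample-size basis. Visits, procedures and data collected do not change. The paired test gives up a little power only if the correlation is near zero (0.61 against 0.65 at n = 12, 2 points, score SD 2).

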## **10. Monitoring and Quality Assurance**

### **a. Independent monitoring of source data**

Experienced study personnel (study monitor) who are not assigned to complete procedures of this study will conduct monitoring after the first subject is enrolled and periodically thereafter. The monitor will be responsible for confirming the completion and correctness of the study procedures as well as record collection and keeping.

### **b. Safety monitoring**

Prior to enrollment, subjects will be screened for eligibility; at which time a complete medical history, including a baseline assessment of the subject's skin will be done. Evaluations will be ongoing throughout the study to detect adverse events and changes in existing medical conditions.

At any time after enrollment, a subject may be discontinued. Reasons for discontinuation of a subject from the study will include, but may not be limited to, the following:

1. Subject is found to be intolerant to a required study procedure at any time point.
2. Subject is noncompliant with protocol restrictions and requirements.
3. Subject develops an intercurrent illness that would, in the judgment of the investigator, affect assessments of clinical status to a significant degree.
4. Subject becomes pregnant while participating in the study.
5. Subject enrolls in another investigational study.
6. Subject requests to withdraw from the study.
7. The study staff decides to suspend or terminate the study.

If possible, a final set of assessments will be performed on all subjects who end their participation prior to study completion.

### **c. Outcome monitoring**

The study will be conducted in accordance with applicable regulations and Good Clinical Practice Guidelines. Keeping files locked with access limited to study staff will ensure confidentiality and data integrity.

### **d. Adverse Event Reporting**

#### *Definition*

Adverse Event (AE) is any untoward medical occurrence in a subject that does not necessarily have a causal relationship with this treatment. An AE can therefore be any unfavorable and unintended sign, symptom, or disease temporally associated with the use of an investigational product, whether or not related to the investigational product.

Serious Adverse Event (SAE) is any untoward medical occurrence that:

- Results in death
- Is life-threatening
- Requires inpatient hospitalization or prolongation of existing hospitalization
- Results in persistent or significant disability or incapacity
- Is a congenital anomaly/birth defect
- Is another medically important condition

*Reporting and Documenting Adverse Events*

All untoward medical occurrences that occur after the subject signs a consent form will be documented as an AE. The Investigator will ensure that all events that occur during the study period are recorded. All AEs will be followed until resolution or until, in the Investigator's judgment, they are chronic and stable. If an emergency situation should occur, appropriate medical measures should be taken to stabilize the subject.

Documentation of AEs includes date and time of onset and resolution of AE, intensity, frequency, seriousness, related interventions, and outcome. The Investigator will also evaluate the probability of a causal relationship of the AE to the study treatment as being: "definite, probable, possible, unlikely, or unrelated." Intensity of adverse events will be graded as mild, moderate, or severe according to the following criteria:

- Mild: symptoms that are easily tolerated and transient in nature with minimal or no impairment of normal activity
- Moderate: symptoms that are poorly tolerated, are sustained, and interfere with normal activity
- Severe: symptoms that are incapacitating and render the subject unable to work or participate in many or all usual activities

All SAEs will be reported to the IRB according to the IRB's requirements.

